5.4.2 TOLERANCE CHALLENGE AT 13 MONTHS

Children in the active group who meet the primary study outcome (desensitised to >1.4g peanut protein at DBPCFC) will then be instructed to stop all peanut exposure (including OIT doses). A further open challenge will be performed after 4 weeks, according to protocol 3, using criteria listed in Section 5.2.2 to determine outcome. Children who tolerate at least 1.4g peanut protein at this challenge will continue with thrice weekly maintenance peanut therapy (4-8 peanuts). Those who react will recommence updosing to the previously tolerated dose and then continue daily maintenance peanut until the 24 months time point.

Protocol 3: Open OFC to roasted PN	Roasted peanut OFC (using defatted flour)		OUTCOME if reacts	
TIME POINT (mins)	Peanut flour	Peanut protein		
0	20	10	RECOMMENCE OIT and updose to previous tolerated dose. Then continue DAILY maintenance of up to 4 peanuts. Repeat tolerance OFC at 24 mths Change to minimum thrice weekly maintenance dose of 4 peanuts.	
30	60	30		
60	200	100		
90	600	300		
120	2000	1000		
150	6000	3000		
Cumulative dose		4440mg	If no reaction:	
2 hour observation period following last dose			Change to thrice weekly maintenance dose of 4-8 peanuts	

5.5 WP2: YEAR 2 OF STUDY

Children in the control group will be offered OIT using boiled PN during months 12-24. An identical protocol to WP1 will be used (section 5.3.3).

Children in the active group (who underwent OIT during months 1-12) will be offered ongoing maintenance therapy, as described above in section 5.4.

5.6 2 YEAR ASSESSMENT

Children who were originally assigned to the control group and who have undertaken OIT during months 12-24 will undergo a further DBPCFC to roasted PN at 24 months. The DBPCFC will be performed as in Section 5.2.2. The purpose of this challenge is to assess for the development of sustained unresponsiveness to roasted peanut following OIT, and the resulting change in threshold of clinical reactivity.

All subjects will also undergo repeat skin prick testing to commercial crude peanut extract and boiled peanut slurry, and quality-of-life assessments as described in section 5.7.1.

All children (in both control and active groups), apart from those who passed the tolerance challenge at 13 months, will be offered a further tolerance challenge at 24 months, to be performed as in section 5.4.

5.7 YEAR 3/4 ASSESSMENTS

All children (in both active and control groups) will be invited to return at the 3 year timepoint for a further set of challenges, to define longer-term tolerance following 2-3 years of active immunotherapy. This is because there is data to suggest that longer duration of OIT is associated with immune memory and more sustained tolerance. These assessments will consist of:

- i. A DBPCFC at the year 3 timepoint (3 years following randomisation) (conducted according to section 5.4.1)
- ii. Open food challenge 4 weeks after stopping OIT (identical to tolerance challenge, section 5.4.2)
- iii. In participants who exhibit sustained unresponsiveness at 4 weeks, a further DBPCFC (conducted according to section 5.4.1) after a further 8 weeks off OIT, to assess for sustained unresponsiveness at 12 weeks.
- iv. In participants who exhibit sustained unresponsiveness at 12 weeks, a further DBPCFC (conducted according to section 5.4.1) after a total of 1 year off OIT, to assess for sustained unresponsiveness at 1 year.

These assessments are summarised in Figure 8.

All families will continue to receive access to the 24/7 helpline during this time. Any participant who reacts at challenge to a previously tolerated level will recommence updosing.

[figure not shown]

Figure 8: Year 3/4 Assessments

Participants who go on to stop all peanut for 12 months (i.e. who pass the 12-week DBPCFC without any loss of tolerance) will be asked to eat 8 roasted peanuts on a monthly basis as a safety measure, to ensure ongoing clinical non-reactivity during this time. Any participant who begins to exhibit symptoms during this 9 month period (prior to final DBPCFC) to the monthly dose of 8 peanuts will be reviewed by the study PI who may take the decision to recommence peanut and not to proceed to the 12 month challenge. This is in order to prevent any participant from reverting back to clinical reactivity that cannot be remedied easily.

5.8 OTHER ASSESSMENTS

5.8.1 ALLERGY SKIN PRICK TESTING

Skin prick testing (SPT) to commercial peanut extract, histamine positive and saline negative control will be performed at baseline, 6, 12, 24 months after starting OIT, and the year 3 assessments (see Fig 8), according to local standard operating procedures consistent with national guidelines.¹³ The baseline SPT will include a modified SPT to boiled peanut.

At the open food challenges (e.g. 6 month challenge), SPT will be performed by an investigator independent to the challenge so as not to influence the interpretation of challenge outcome. Additional positive controls will be included as needed to ensure blinding of the participant.

¹³ http://www.bsaci.org/Guidelines/Skin_Prick_Testing.pdf

5.8.2 QUALITY OF LIFE ASSESSMENTS

The impact of OIT on participants' quality of life (QoL) will be assessed both from parents' and participants' perspective using abbreviated versions of disease-specific validated "food-allergy quality of life questionnaire" (FAQL-Q) in its parental, ¹⁴ child¹⁵ and teenage¹⁶ forms at baseline, 3, 6, 12, 24 and 36 months in both the active and control groups. These new abbreviated versions have been validated (data submitted for publication). We will also assess the impact of the child's food allergy on parent QoL, using the FAQL-Parent Burden form (which has been validated in a UK population).¹⁷ QoL assessments will be done both prior to and after oral challenges.

The FAQL-questionnaires are based on a 7-point Likert scale and changes greater than 0.5 points over time have been defined as clinically significant. Previous studies have reported a positive effect on QoL following OIT to peanut from the parents' perspective, however, there are no controlled studies which have addressed the impact on QoL as perceived by participants. This is a significant knowledge gap, since there is a concern that while parents report an improved QoL when their child undergoes OIT, the child themselves may experience a worsening of QoL due to frequent side effects and need to alter their activities following OIT doses.

In line with current expert opinion, and to ensure the ability to compare responses consistently during the first 12 months of OIT, children who are age 12 at study commencement will be asked to complete the Teenage versions of the QoL assessments, unless there are difficulties with comprehension which preclude this.

We will also assess parental anxiety before, and 12 and 24 months after their child commencing OIT, using the Perceived Stress Scale.¹⁹

In subjects who fail visit 3 (tolerance check to boiled peanut) or are withdrawn during the active OIT phase due to a significant allergic reaction, we will contact the family at 1 and 6 months after the event to repeat the QoL assessments. This will allow us to assess the impact of 'failing' OIT on the young person and their family. In addition, at both time points, we will ask the family if we can arrange a convenient time when we can undertake a limited structured telephone interview (10-15 minutes) with the parent/guardian(s) and their child, to explore any issues which might have been raised as a result of the reaction, following the outline in Appendix 3. The answers to these questions will be documented and analysed using the framework method.²⁰

It is therefore important for this study to include mechanistic assessments to allow for markers of successful desensitisation to be assessed, in order to improve the efficacy of future OIT protocols. We will include a series of laboratory assessments in subjects undergoing OIT, allowing longitudinal comparisons to be made in those undergoing OIT (vs controls) to assess the following:

- Changes in serum specific antibodies pre- and post-OIT: Total IgE; specific IgE, IgG4 to whole peanut and peanut components (Ara h 1, 2, 3, 8 and 9) and their ability to cause an effector cell response will be measured
- IgE-immunoblot using patient sera to identify in vitro the binding of participants IgE to peanut proteins, and how this varies during OIT.
- Identification of serum factors associated with the development of oral tolerance during peanut OIT, by means of a validated IgE facilitated-binding assay.
- Changes in basophil responses (assessed by CD63 and CD203c expression by flow cytometry) following *in vivo* and *ex vivo* peanut stimulation, and how these vary during OIT. Confirmatory work will be performed in a subset of patients using purified basophils isolated from whole blood.
- Biomarkers that may identify successful tolerance induction to peanut
- Changes in T and B cell populations and their immune profile during OIT, including allergen-specific proliferation of T-cell subtypes (including T helper and regulatory T cells) and changes in immunoglobulin repertoire by peanut-specific B-cells.
- mRNA expression and methylation of proteins (such as forkhead box protein 3 (FOXP3) sites) on T cell subsets which may predict the presence of sustained unresponsiveness.

These assessments will be performed on blood samples taken at baseline, 3, 6, 12, 13 and 24 months, as well as at the 3 year assessments (outlined in Figure 8) after commencement of OIT. Laboratory work will be initially performed at the National Heart & Lung Institute, Imperial College London, although some assays may be performed elsewhere in the UK or abroad, where lack of local expertise necessitates this). Specimens may also be stored for future use in new assays to measure immune responses or biomarkers, as research tests are developed.

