1.2 STUDY RATIONALE & JUSTIFICATION

We wish to formally assess, in a randomized controlled study, whether a modified approach using boiled peanut for peanut OIT can result in desensitisation and sustained unresponsiveness (i.e. tolerance) to roasted peanut. We will assess the safety of this approach, and study the immunological mechanisms involved, our secondary aim being to develop clinically-useful predictors for identifying individuals likely to undergo successful desensitization.

STUDY HYPOTHESIS:

A pragmatic protocol utilizing increasing doses of boiled peanut can induce desensitisation to roasted peanut, in peanut-allergic individuals, with an acceptable safety profile.

¹Turner PJ, Gowland MH, Sharma V, et al. Increase in anaphylaxis-related hospitalizations but no increase in fatalities: An analysis of United Kingdom national anaphylaxis data, 1992-2012. JACI 2014; doi: 10.1016/j.jaci.2014.10.021.

²Bégin P, Paradis L, Paradis J, Picard M, Des Roches A. Natural resolution of peanut allergy: a 12-year longitudinal follow-up study. JACI In Practice 2013;1:528-30.e1-4.

³Wood RA, Sampson HA. Oral immunotherapy for the treatment of peanut allergy: is it ready for prime time? IACI In Practice 2014;2:97-8.

⁴Vickery BP, Scurlock AM, Kulis M, et al. Sustained unresponsiveness to peanut in subjects who have completed peanut oral immunotherapy. JACI 2014;133:468-75.

⁵Tang ML, Ponsonby AL, Orsini F, et al. Administration of a probiotic with peanut oral immunotherapy: A randomized trial. J Allergy Clin Immunol. 2015. doi: 10.1016/j.jaci.2014.11.034.

⁶Turner PJ, Mehr S, Sayers R, et al. Loss of allergenic proteins during boiling explains tolerance to boiled peanut in peanut allergy. JACI 2014;134:751-3.

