2.2 SECONDARY OBJECTIVES

- To evaluate the safety of peanut OIT in children with IgE-mediated peanut allergy.
- To assess the rate of sustained unresponsiveness following peanut OIT
- To identify predictors which can identify individuals likely to undergo successful desensitization and sustained unresponsiveness using boiled peanut
- To assess the impact of peanut OIT on quality of life (QoL) measures, both from the child/young person's perspective as well as their parents'.
- To assess how duration of OIT impacts on sustained unresponsiveness

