7.2.2 ANALYSIS OF SECONDARY ENDPOINTS

The following secondary analyses will be performed, using two-sided testing for non-parametric data at a p<0.05 level of significance:

- Relative change in clinical threshold (NOAEL, LOAEL) to roasted peanut at 6 and 12 months in active vs control, using Mann-Whitney U test.
- Proportion of subjects who tolerate 1.4g (or more) roasted peanut protein in the active and control groups, 12 months after randomization and following cessation of all peanut intake for 4 weeks after 1 and 3 years of OIT, using a two-sided Fisher's exact test at a p<0.05 level of significance.
- Change in quality of life assessments before, and at 6 and 12 months after OIT, as assessed by FAQL-Questionnaire in children, teenagers and their parents in the active vs control groups using paired and group comparisons by non-parametric testing.
- The incidence of adverse events experienced between active and control groups. Statistical differences will be
 determined using Fisher's exact test for proportions or using non-parametric tests for graded reactions.
 Logistic regression will be used to assess the influence of age, gender, asthma status and prior history of
 anaphylaxis on incidence of adverse events.
- Immunological outcome measures pre-, during and post- 12 months of OIT, using Mann-Whitney U test (for paired comparisons) or Friedman's test (for trends over time).

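### Secondary objective 2.2 seeks predictors of desensitisation and sustained unresponsiveness, but no line in 7.2.2 relates any marker to challenge outcome

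*Combined protocol and SAP*

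**What the plan says.** The aim appears in three places. Section 2.2 lists it as a secondary objective: "To identify predictors which can identify individuals likely to undergo successful desensitization and sustained unresponsiveness using boiled peanut". Section 1.2 goes further: "our secondary aim being to develop clinically-useful predictors for identifying individuals likely to undergo successful desensitization". Section 5.8.3 repeats it for the laboratory work ("It is therefore important for this study to include mechanistic assessments to allow for markers of successful desensitisation to be assessed") and describes the T-cell mRNA and methylation assays as ones "which may predict the presence of sustained unresponsiveness". The comparison that 5.8.3 names is longitudinal, by treatment: "allowing longitudinal comparisons to be made in those undergoing OIT (vs controls").

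The analysis is in 7.2.2. The whole provision for immunology is "Immunological outcome measures pre-, during and post- 12 months of OIT, using Mann-Whitney U test (for paired comparisons) or Friedman's test (for trends over time"). The only regression model is "Logistic regression will be used to assess the influence of age, gender, asthma status and prior history of anaphylaxis on incidence of adverse events".

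The plan also names a candidate predictor. Sections 3.2 and 5.3.2 expect children sensitised mainly to Ara h 2 to do better, 5.3.2 defines that phenotype by IgE cut-offs, and randomisation is stratified on it. Section 7.2 does not analyse it against outcome.

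**The concern.** Prediction needs a marker on one side and success or failure among treated children on the other. The immunology line has the first without the second. It asks whether a marker changes during OIT, and 5.8.3 itself says such changes accompany immunotherapy and are often transient. A significant trend is therefore expected and does not show who will succeed.

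Two things are at stake. If 7.2.2 is followed literally, a listed objective is left unanswered, although the samples and challenges needed to answer it are already planned. If the team fills the gap after seeing the data, the choice of markers, time points and outcome is open, and with so few children some apparent predictors would arise by chance.

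**Working it through.** **The plan's own figure.** Section 7.1 gives 46 children (30 active, 16 control) for 60% v 10%, 2:1, two-sided 0.05, 80% power, continuity correction and 20% loss. The pooled proportion is (0.10 + 2×0.60)/3 = 0.433. Control n before correction = [1.96√(0.433×0.567×1.5) + 0.842√(0.10×0.90 + 0.60×0.40/2)]² / 0.50² = 9.92. With correction, n = (9.92/4)×[1 + √(1 + 3/(9.92×0.50))]² = 12.75, total 38.25. Multiplying by 1.2 gives 45.9, which matches 46; dividing by 0.8 gives 47.8. The figure reproduces, but it concerns active v control and says nothing about predictors.

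**What each line of 7.2.2 compares.**

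| Line in 7.2.2 | Comparison | Uses a marker? | Compares successes with failures among treated children? |
|---|---|---|---|
| Threshold | active v control | no | no |
| Tolerating 1.4 g | active v control | no | no |
| Quality of life | paired, and active v control | no | no |
| Adverse events | active v control; logistic regression on clinical covariates | no | no |
| Immunology | before, during and after OIT | yes | no |

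No line has a yes in both right-hand columns.

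**Why a time trend cannot stand in.** Suppose a marker rises by the same amount in all 30 active children. A sign test gives p = 2×0.5³⁰, about 2×10⁻⁹. The rise is identical in successes and failures, so its AUC for success is 0.5.

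**Numbers available for the missing comparison, at 60% success.**
- All 30 active children: 30×0.6 = 18 v 12.
- After 20% loss, 24 children: 14.4 v 9.6, about 14 v 10.
- All 46 treated, if every control takes up OIT in year 2 with no loss: 27.6 v 18.4, about 28 v 18.

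For one normally distributed marker (Mann-Whitney with efficiency 0.955, two-sided 0.05, 80% power, AUC = Φ(d/√2)), the smallest detectable difference is:
- 18 v 12: 1.11 SD (AUC 0.78)
- 14 v 10: 1.25 SD (AUC 0.81)
- 28 v 18: 0.89 SD (AUC 0.73)

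Only large differences are within reach, before any adjustment for multiple markers.

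**Illustration of an unplanned search.** The first bullet of 5.8.3 contains total IgE, plus IgE and IgG4 to whole peanut and five components: 1 + 2×(1+5) = 13 measures. If none is predictive and they are independent, the chance that at least one reaches p<0.05 is at most 1 − 0.95¹³ = 0.49. Simulated Mann-Whitney tests at 18 v 12 give about 0.47-0.48 at correlation 0, 0.33-0.34 at 0.5, 0.20 at 0.8 and 0.14-0.16 at 0.9. The documents give no correlations, so the range is about 14-48%.

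**Sustained unresponsiveness.** Under 5.4 and 5.4.2 only children who tolerate the 1.4 g threshold at 12 months go on to the 13-month challenge, about 18 of 30. Sections 3 and 5 describe the four-week stop for the active group without that restriction. A predictor analysis therefore has no defined denominator until one is stated.

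**The case against.** The best defence has four parts.

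First, the outcome listed in 3.1.2 is immunological measures before, during and after OIT, and 7.2.2 does analyse that. This stands: the gap is in an objective for which no outcome is listed, not in a listed outcome left without a test.

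Second, much of 5.8.3 is about mechanism, where change over time and comparison with controls are relevant. This also stands, and it is why the conflict rests on 2.2 against 7.2.2 more than on 5.8.3. A comparison with controls shows that OIT moves a marker, however, not which treated children will succeed.

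Third, Mann-Whitney U compares two independent groups, so a reader might infer that a comparison of responders with non-responders was intended. The text assigns the test to paired comparisons and names no responder grouping. The line is internally inconsistent, which is a separate error, and it cannot be read as a planned predictor analysis.

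Fourth, this is early mechanistic work with hedged wording, and future assays cannot all be prespecified. That is a fair reason to keep most markers exploratory. It does not excuse leaving out the comparison itself, since 1.2 claims clinical usefulness and 2.2 does not call the aim exploratory.

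A reader might also infer that 7.2.2 only ever tests change within children. It does not: the other lines compare active with control.

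**Conclusion.** The point holds as a mismatch between a named secondary aim and the planned analysis. This follows from the text and needs no numerical assumption. The group sizes rest on the plan's 60% success rate and 20% loss; the detectable differences also assume a normally distributed marker.

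The 14-48% figure illustrates what an unplanned search of 13 antibody measures could produce, under assumed correlations of 0.9 down to 0. It should not be read as the plan's error rate, because the plan does not propose such a search. Nor does the gap reach the primary comparison, which is separate and unaffected. This should be corrected, at the level of a secondary objective.

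**What to change.** Add a bullet to 7.2.2:
- Among OIT-treated children, compare pre-OIT marker values between those who do and do not tolerate 1.4 g at the DBPCFC after 12 months of OIT. State how children without that challenge are counted.
- Name the Ara h 2-predominant phenotype, as defined in 5.3.2, as the one prespecified predictor. Report an odds ratio and 95% CI from exact or Firth logistic regression. The documents do not give the phenotype's frequency, so its precision cannot be worked out in advance; expect a wide interval.
- Treat all other 5.8.3 markers as exploratory, with false-discovery-rate control.
- For sustained unresponsiveness, state the denominator: either only children who take the 13-month challenge (about 18 of 30 at 60% success), or all OIT starters, with those not desensitised at 12 months counted as not having it.
- Control children who take up OIT in year 2 may be added as a supporting analysis, using values from before their own OIT.

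Keep the tests over time as description, and replace Mann-Whitney U with a paired test wherever the comparison is within child. In 1.2, replace the promise to develop clinically useful predictors with an aim to explore candidate predictors.

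The cost is some SAP wording and a little extra analysis on samples and challenges already planned. The downside is a more modest claim about predictors.

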5.9 STUDY COMPLETION

The study duration is for up to 4 years following randomisation, as outlined in section 5.7. The study will be considered complete following enrolment of the last patient and completion of the study procedures in that patient.

At the end of the study, children will be re-integrated into the routine clinical allergy service for ongoing care.

5.9.1 EARLY STUDY TERMINATION

An Independent Data Monitoring Committee (IDMC) will assess study safety on a regular basis. The IDMC has the authority to suspend the study, or request withdrawal of a particular participant, at any stage if it concludes there are significant safety concerns affecting a single participant or the study as a whole.

Recruitment to the study, and further peanut challenges and updosing, will be suspended pending review by the IDMC in the event of:

- any death
- a participant being admitted to the intensive care unit for a study-related adverse event
- a participant experiencing a life-threatening anaphylactic reaction to an OIT dose.

The IDMC will consider the circumstances and make a recommendation as to whether to terminate the study, or continue with or without a protocol amendment.

6. ADVERSE EVENT REPORTING

6.1 DEFINITIONS

An adverse event is any occurrence or worsening of an undesirable or unintended sign, symptom, laboratory finding, or disease that occurs during participation, including occurrences that are not necessarily caused by or related to a study intervention. An adverse event will be followed until it resolves or until 30 days after a participant terminates from the study, whichever comes first.

A **serious adverse event** (SAE) is defined as any adverse event that suggests a significant hazard. This includes but is not limited to any of the following:

- 1. Death: Any death that occurs during the study must be reported whether considered treatment related or not.
- 2. A life-threatening event: Any adverse therapy experience that, in the view of the investigator, places the participant at immediate risk of death from the reaction as it occurred.
- 3. Inpatient hospitalization or prolongation of existing hospitalization.
- 4. Persistent or significant disability.
- 5. An event that requires intervention to prevent permanent impairment or damage. An important medical event that may not result in death, be life threatening, or require hospitalization may be considered an SAE when, based on appropriate medical judgment, it may jeopardize the participant and may require medical or surgical intervention to prevent one of the outcomes listed above.
- 6. Important AEs that are not immediately life-threatening or do not result in death or hospitalization but may jeopardise the subject or may require intervention to prevent one of the other outcomes listed in the definition above, should also be considered serious.

The adverse event can be described as 'expected' if it caused symptoms and/or signs that could be reasonably described as a consequence of an allergic reaction to peanut exposure within the protocol. Symptoms of an allergic reaction are defined as any described within this protocol.

An adverse event is considered "unexpected" when its nature or severity is not consistent with the investigator's protocol.

An adverse event is defined as "**related**" when it has resulted from the administration of any of the research procedures. Related adverse events are defined as "**adverse reactions**".

Any symptoms requiring treatment for anaphylaxis (adrenaline, steroids, salbutamol) following an OIT dose will be classified as a SERIOUS ADVERSE REACTION.

